15.4 Personal information of the research subjects

The sponsor or the designee shall affirm the principle of the protection of research subjects' private/personal information. Throughout this study, research subject ID numbers shall be used to link the subject's source data to the sponsor's research database and research-related documents. Limited information on research subjects such as gender, age, and date of birth may be used within the scope of all applicable laws and regulations for identification of research subjects and confirmation of accuracy of research subject ID number.

For verification of the conduct of the research in compliance with this protocol and the Ethical Guidelines for Medical and Health Research Involving Human Subjects, the sponsor shall require the principal investigator to provide the research sponsor's designee, representatives of regulatory authorities, designated auditors, and committees such as the Ethical Review Board direct access to research subjects' original medical records (source data or documents), including laboratory test results, admission and discharge records during a subject's research participation, and autopsy reports. The principal investigator or investigator shall obtain specific authorization of the research subject as part of the informed consent process for access to research subject's original medical records by research sponsor's designee and representatives of regulatory authorities (see Section 15.3).

When providing a copy of source documents to the sponsor, the principal investigator or investigator shall delete information that may lead to identification of an individual (name and address of research subject, other personal information not recorded on the CRF of the research subject).

15.5 Consultation windows for the research subjects or persons related to the research concerned

The principal investigator shall establish a contact service to respond to inquiries concerning this clinical research from research subjects or concerned people. Details of the contacts for inquiries will be described in the ICF.

15.6 Financial burden or reward to the research subjects

Of the expenses for this clinical research, the sponsor shall offer compensation for medical treatment not covered by health insurance as research expenses. The research subjects shall pay expenses for medical treatment covered by ordinary health insurance.

In addition, the principal investigator shall pay expenses such as transportation expenses for participation in this clinical research to the research subjects at each visit from the research funds. Details of the financial burden on the research subjects and rewards shall be described in the informed consent form and information sheet.

15.7 Benefits and inconveniences to the research subjects

15.7.1 Benefits to research subjects

By participating in this clinical research, the research subjects may understand one's own condition of vascular endothelial function in detail.

15.7.2 Inconveniences to research subjects

By participating in this clinical research the burden of the research subject may increase as number of visits will increase compared to daily medical care.

15.8 Attribution of research results and access rights

15.8.1 Attribution of research results

The research results and data obtained from this research shall belong to the sponsor.

15.8.2 Data access rights

Access rights for all data and information generated from this research will be given to personnel approved by the sponsor. In addition, secondary use (meta-analysis, etc.) of the data obtained in this clinical research may be possible if used in such a way that the data shall not be linked to personal identification information.

15.9 Reporting of results, Publication, disclosure, and clinical research registration policy

15.9.1 Reporting of results, publication and disclosure

The principal investigator shall report a written summary of results of the research to the chief executive of the study site and provide the sponsor with all the results and data obtained from the research. Only the sponsor may disclose the research information to other principal investigators, investigators or regulatory authorities during the research period, except when required by laws and

regulations. The sponsor shall be responsible for publication of the research protocol and research-related results (including the public web site) except for other cases permitted in the research contract.

During research period and after the end of research, the sponsor or the designee should promptly summarize the results and present it to medical journals and academic conferences, etc. The sponsor may publish any data or information obtained from the research (including data and information provided by the principal investigator) without obtaining agreement of the principal investigator.

The investigator or the subinvestigator should obtain the prior written approval from the sponsor when publishing the information obtained in this research at an academic conference, etc.

15.9.2 Clinical research registration

To ensure that information on clinical research is made accessible to the public in a timely manner and to comply with applicable laws, regulations, and guidelines, Takeda Pharmaceutical Company Limited shall register all clinical research being conducted in patients around the world at public trial registration sites, including at least the website(s) of ClinicalTrials.gov (and) Japan Pharmaceutical Information Center Clinical Trials Information (JAPIC), before initiation of the clinical research. On such websites, the research location (city, country), subject recruitment status, and contact information for Takeda Pharmaceutical Company Limited are open to the public.

15.9.3 Clinical trial results disclosure

Takeda Pharmaceutical Company Limited shall post the research results, irrespective of the nature of the results, at the public trial registration site(s) of ClinicalTrials.gov (and) JAPIC in accordance with applicable laws and regulations.

15.10 Insurance and compensation for injury

In case of injuries, each research subject in the clinical research must be insured in accordance with the regulations applicable to the study site where the subject is participating. The sponsor or the designee shall buy an insurance policy to compensate for health injury in research subjects.

Healthy injury in a research subject will be compensated as specified in the study contract.

Compensation-related questions by the principal investigator or investigators should be made to the sponsor or the designee.

Appendix A Schedule for Research Procedures

Time of visit	Week Day	Observation period	Treatment period			Discontinuation ^(h)
		-4 -29	0 -1 ^(g)	4 28	8 56	
Allowable range (Day)		-29 to -1	-15 to -1	14 to 41	42 to 70	Up to 3 days after the last dose
VISIT Number		1	2	3	4	
Informed consent procedure		X				
Inclusion/Exclusion criteria		X	X			
Demographic data, medical history, previous therapeutic drugs		X	X ⁽ⁱ⁾			
Physical examination		X ^(e)	X	X	X	X
Confirmation of food and drink consumption before visit ^(a)		X	X	X	X	X
Height		X				
Body weight		X				
BMI		X				
Vital signs		X ^(e)	X	X	X	X
Concomitant drugs ^(b)		X ^(e)	X	X	X	X
Concurrent disease		X ^(e)	X			
Laboratory tests ^(c)						
Serum chemistry (fasting)		X ^(e)	X	X	X	X
Serum chemistry (4 h postprandial) ^(d)			X	X	X	X
Urinalysis (fasting)		X ^(e)	X	X	X	X
Other tests			X	X	X	X
FMD						
FMD (fasting)			X ^(f)	X ^(f)	X ^(f)	X ^(f)
FMD (4 h postprandial) ^(d)			X ^(f)		X ^(f)	X ^(f)
Prescription of the study drug			X	X		
Drug compliance				X	X	X
PTE and adverse events assessment		(X)	←X→	←X→	←X	←X

(a) Eating/drinking to excess and extreme change in dietary content should be avoided on the day before the hospital visit.

(b) All concomitant drugs will be recorded.

(c) Hematology, urinalysis, and other details will be entered below:

- Hematology

(Fasting): TG, total cholesterol, LDL-cholesterol, HDL-cholesterol, Remnant-like particle (RLP) cholesterol, apoprotein B-48, C-reactive protein (CRP), fasting plasma glucose (FPG), plasma fatty acid fraction

(4 hours postprandial): TG, total cholesterol, LDL-C, HDL-cholesterol, Remnant-like particle (RLP) cholesterol, apoprotein B-48

- Urinalysis: Quantitative 8-epi-PGF2 α

(d) Time window \pm 30 minutes

(e) To be performed before test at Visit 2

(f) To be performed by the physician or the clinical laboratory technician who has finished the FMD measurement training

(g) To be performed after consent has been obtained. Medication will be started the day after the completion of all the tests of Week 0. The start date of medication will be referred to as day 1.

(h) To be performed to the extent possible

Appendix B Responsibilities of the Principal Investigator

1. Appropriately To appropriately conduct the clinical research in compliance with this research protocol and the Ethical Guidelines for Medical and Health Research Involving Human Subjects and with the highest respect for human rights, safety, and welfare of research subjects.
2. Prepare To prepare a list of any other investigators and/or research collaborators when certain important research-related activities are divided by investigators and/or research collaborators, and submit the list to the sponsor as required.
3. To prepare the informed consent form and revise it as necessary.
4. To check the contents of the study contract.
5. To provide sufficient information on the protocol, drug and duties of each personnel to subinvestigators and study collaborators, and give guidance and supervision.
6. To select research subjects who satisfy the inclusion criteria, give explanation using written information, and obtain consent in writing.
7. To be responsible for all medical judgments related to the research.
8. Corresponding to request from the chief executive of the study site, to report the latest progress status at least once a year to the chief executive of the study site.
9. To confirm and comprehended the most update status regarding the COI of the investigators participating in the clinical research according to the study site.
10. To ensure, together with the chief executive of the study site, that sufficient medical care is provided to research subjects for all research-related clinically problematic adverse events throughout the period of subjects' research participation and thereafter.
11. When a research subject is treated at another medical institution or department, to inform the acting physician at the medical institution or department in writing of the research subject's study participation and research completion/discontinuation after obtaining the research subject's consent, and prepare a record.
12. When emergency reporting of serious adverse events, etc., is required, to immediately report it in writing to the chief executive of the study site and the sponsor.
13. Prepare correct and complete CRFs, and submit them to the sponsor with an electronic signature.
14. To verify any entries on the CRFs prepared by the investigator or transcribed by the collaborator from source data, {electronically sign/ sign or write name/affix a seal, and submit them to the sponsor.
15. To discuss a revision of the protocol, etc., when proposed by the sponsor.
16. To report the research completion in writing to the chief executive of the study site.

| 8.2. Other Endpoints and the Analytical Methods | 12 |
| 9. LISTING..... | 13 |
| 10. CONSIDERATIONS on STATISTICAL ANALYSIS..... | 14 |
| 10.1. Adjustments for Covariates | 14 |
| 10.2. Handling of Dropouts or Missing Data..... | 14 |
| 10.3. Criteria for Interim Analysis and Early Discontinuation | 14 |
| 10.4. Multicenter Studies..... | 14 |
| 10.5. Multiple Comparisons/Multiplicity | 14 |
| 10.6. Examination of Subgroups | 14 |
| 11. REVISION HISTORY | 15 |

1. DEFINITIONS of TERMS

- Summary Statistics: Number of subjects, mean, SDs, maximum values, minimum values, and quartiles
- Treatment Group: Omega-3-acid ethyl esters 2g, Omega-3-acid ethyl esters 4g

2. TIME WINDOW

For each inspection, observation and evaluation item, evaluable data is handled according to the following table. When there are multiple data that can be evaluated at the same visit, the one with the closest inspection date, observation, and evaluation date to the reference date is adopted, and if the difference from the reference date is the same, the later data is adopted.

< FMD (Fasting, 4h postprandial) >

| Visit | Reference implementation date | Time Allowance |
|---------------------------|-----------------------------------|-------------------------------|
| | | Days after the Administration |
| Start of Treatment Period | Days after the Administration: -1 | -15 to -1 |
| Treatment period 4 week | Days after the Administration: 28 | 1 to 41 |
| Treatment period 8 week | Days after the Administration: 56 | 42 to 70 |

< Other than FMD >

| Visit | Reference implementation date | Time Allowance |
|---------------------------|-----------------------------------|-------------------------------|
| | | Days after the Administration |
| Start of Treatment Period | Days after the Administration: -1 | -29 to -1 |
| Treatment period 4 week | Days after the Administration: 28 | 1 to 41 |
| Treatment period 8 week | Days after the Administration: 56 | 42 to 70 |

- The reference implementation date and the number of days after administration in the treatment period are indicated as “Day -1” for the day before study drug administration and “Day 1” for the administration day. As the administration is started from the day after the visit, 4 weeks of the treatment period and 8 weeks of the treatment period are 28 days and 56 days after the study drug administration.

3. ANALYSIS SET

- Full Analysis Set

The subjects who were randomized and given at least one dose of the study drug.

- Safety Analysis Set

The subjects who are given at least one dose of the study drug.

4. CONSIDERATIONS for ANALYSIS

- Confidence coefficient

95% (two-sided estimation)

- Display digit

[Mean, Confidence coefficient, Quartiles]

Round statistics off to the 1 digits lower than significant digits of the data.

[Standard Deviation]

Round statistics off to the 2 digits lower than significant digits of the data.

[Minimum and Maximum Values]

Display the data at the significant digits.

[Proportion, Percentage]

Round statistics off to 1 decimal places.

5. OTHER DATA HANDLING

[Data Handling for Study Drug]

- Duration of Treatment

Duration of Treatment = Date of the Last Dose - Date of the First Dose + 1

[Data Handling for Adverse Event]

- Adverse Events

An adverse event is defined as any untoward medical occurrence in a patient or a subject receiving a pharmaceutical product (including the study drug). It does not necessarily have an apparent causal relationship with this pharmaceutical product (including study drug).

- Time to Occurrence of Adverse Event

Time to Occurrence of Adverse Event = Onset Date of Adverse Event - Date of the First Dose + 1

- Non-serious Adverse Events

Adverse events, excluding serious adverse events (protocol 10.1.4), shall be non-serious adverse events in the case of an incidence of over 5% in at least one treatment group.

[Data Handling for Duration of Dyslipidemia (year)]

- Duration of Dyslipidemia (year)

Duration of Dyslipidemia (year) = (Date of Informed Consent (year/month) – Onset Date of Dyslipidemia (year/month)) / 12 (rounded off to two decimal places)

If only the month of the onset of dyslipidemia is unknown, the month of the onset of dyslipidemia is regarded as “January”.

6. SUBJECTS, DEMOGRAPHIC and OTHER BASELINE CHARACTERISTICS

6.1. Subject Disposition

6.1.1. Study Information

Analysis Set: All subjects who were obtained informed consent

Analysis Variables: The earliest date of informed consent

The latest date of the last date of administration

Version of MedDRA

Version of SAS

Analysis Methods: For the above analysis variables, the following analysis is performed.

(1) Show above items.

6.1.2. Eligibility of Subjects

Analysis Set: All subjects who were obtained informed consent

Analysis Variables: Randomization into the treatment period of the study

[Yes, No (and the reason)]

Analysis Methods: For the above analysis variables, the following analysis is performed.

(1) Frequency Count

6.1.3. Subject Disposition

6.1.3.1. Study completion status

Analysis Set: Randomized subjects

Analysis Variables: Study completion status

[Complete, Incomplete (and the reason)]

Analysis Methods: For the above analysis variables, the following analysis is performed for each treatment group and all subjects in the analysis set.

(1) Frequency Count

6.1.4. Protocol Deviations and Analysis Datasets

6.1.4.1. Protocol Deviations

Analysis Set: Randomized subjects

Analysis Variables: Protocol Deviations

[Major GCP Violations, Deviations of Protocol Entry Criteria, Deviations of Discontinuation Criteria, Deviations Related to Treatment Procedure or Dose, Deviations Concerning Excluded Medication or Therapy, Deviations to Avoid Emergency Risk, Other Deviations]

Analysis Methods: For the above analysis variables, the following analysis is performed for each treatment group and all subjects in the analysis set.

(1) Frequency Count

Summarize the number of subjects who have deviated from the protocol, classify the deviations into above category, and show the breakdown of deviations. Subjects applicable for multiple categories will be counted once in each category.

6.1.4.2. Datasets Analyzed

Analysis Set: Randomized subjects

Analysis Variables: Subjects excluded from analysis datasets

[Reason of exclusion]

Full Analysis Set [Adopted]

Safety Analysis Set [Adopted]

Analysis Methods: For the above analysis variables, the following analysis is performed for each treatment group (both (1) and (2)) and all subjects (for (2)) in the analysis set. For analysis (1), Subjects applicable for multiple categories will be counted once in each category.

(1) Frequency count in each analysis set about handling for subjects

(2) Frequency count in each analysis set of adopted subjects.

6.2. Demographics and Other Baseline Characteristics

6.2.1. Distribution of Demographics

Analysis Set: Safety Analysis Set

Analysis Variables:

Age (years old) [Min<= - <65, 65<= - <75, 75<= - <=Max]

Sex [Male, Female]

Height (Observation period) (cm)

[Min<= - <150, 150<= - <160,
160<= - <170, 170<= - <=Max]

Weight (Observation period) (kg)

[Min<= - <50.0, 50.0<= - <60.0,
60.0<= - <70.0, 70.0<= - <80.0,
80.0<= - <=Max]

BMI (Observation period) (kg/m²)

[Min<= - <18.5, 18.5<= - <25.0,
25.0<= - <=Max]

Duration of Dyslipidemia (year)

[Min<5, 5<=Max, Unknown]

Last Menstrual Period

[<2 years, 2 years <=, Not Applicable]

Frequency of Consumption of Fish

[Almost every day, About Every Two Days, About
Once or Twice Per Week, Rarely]

Smoking Classification

[Never Smoked, Current Smoker, Ex-Smoker]

Drink Alcohol Almost Every Day?

[Yes, No]

TG level (fasting) (Start of Treatment Period) (mg/dL)

[Min<= - <200, 200<= - <500, 500<= - <=Max]

TG level (4h postprandial) (Start of Treatment Period) (mg/dL)

[Min<= - <200, 200<= - <500, 500<= - <=Max]

Plasma Fatty acid Fraction EPA/AA ratio (Start of Treatment Period)

[Min<0.3, 0.3<=Max]

Analysis Methods: For the above analysis variables, the following analysis is performed for each treatment group and all subjects in the analysis set.

- (1) Frequency count for discrete variables and summary statistics for continuous variables

6.2.2. Medical History and Concurrent Disease

Analysis Set: Safety Analysis Set

Analysis Variables: Medical history, Concurrent disease

Analysis Methods: For the above analysis variables, the following analysis is performed for each treatment group. Analysis variables will be coded using the MedDRA dictionary and be summarized into SOC and PT. SOC's will be sorted in alphabetical order, then PTs will be sorted in frequency order.

- (1) Frequency of medical history by SOC/PT
- (2) Frequency of concurrent disease by SOC/PT

The method of accounting for the frequency is as follows.

[Number of Subjects]

Within each summary, subjects with one or more events within a level of SOC term is counted only once in that level. Similarly, subjects with one or more events within a level of PT term is counted only once in that level.

6.2.3. Prior and Concomitant Medication

Analysis Set: Safety Analysis Set

Analysis Variables: Prior medication
Concomitant medication

Analysis Methods: For the above analysis variables, the following analysis is performed for each treatment group. Analysis variables will be coded using the WHO (World Health Organization) Drug. Coded medications will be sorted in frequency order. Medications used more than once within a subject will be counted only once for the subject.

- (1) Frequency of prior medication
- (2) Frequency of concomitant medication which was completed administration before study drug administration
- (3) Frequency of concomitant medication which was started administration before study drug administration and was continued administered after start of study drug administration
- (4) Frequency of concomitant medication which was started administration after start of study drug administration

- (5) Frequency of concomitant medication which was administered study drug administration period.

6.3. Treatment Compliance

6.3.1. Study Medication Compliance

Analysis Set: Safety Analysis Set

Analysis Variables: Study medication compliance

[Min<= - <50.0%,
50.0%<= - <=Max]

Visit: Treatment Period 4 week and 8 week

Analysis Methods: For the above analysis variables, the following analysis is performed for each treatment group and all subjects in the analysis set by visit.

- (1) Frequency Count

6.3.2. Food and Drink Consumption before the Visit

Analysis Set: Safety Analysis Set

Analysis Variables: Did you consume alcohol from 9:00 pm two days before the hospital visit to the time of the fasting test, or consume food from 9:00 pm on the day before to the time of the fasting test?
[Yes, No]

Did you experience excess and extreme change of dietary content (Eating/Drinking) on the day before the fasting test.
[Yes, No]

Visit: Treatment Period 4 week and 8 week

Analysis Methods: For the above analysis variables, the following analysis is performed for each treatment group and all subjects in the analysis set by visit.

- (1) Frequency Count

6.3.3. Study Medication Exposure

Analysis Set: All Subjects Administered

Analysis Variables: Duration of exposure (days)

[1<= - <29, 29<= - <57, 57<= - <=Max]

Analysis Methods: For the above analysis variables, the following analysis is performed for each treatment group and all subjects in the

analysis set.

- (1) Frequency count for discrete variables and summary statistics for continuous variables

7. EFFICACY EVALUATIONS

7.1. Primary Endpoint and the Analytical Methods

Analysis Set: Full Analysis Set

Analysis Variables: %FMD (fasting)

Visit: Start of Treatment Period, Treatment Period 4 week and 8 week

Stratification Factor: Fasting TG at Observation Period

[150<= - <200, 200<= - <500]

Analysis Methods: For the above analysis variables, the following analysis is performed.

- (1) Summary statistics by treatment group and a two-sided 95% confidence interval for the mean will be calculated at each visit during the treatment period, and a diagram illustrating the change in the mean \pm SD will be prepared.
- (2) The change for each treatment group (Treatment Period 4 week/8 week – Start of Treatment Period) will be calculated at each visit during the treatment period and the same analysis as in (1) will be performed.
- (3) Summary statistics using stratification factor and two-sided 95% confidence interval (CI) of mean value by visit will be calculated by treatment group.
- (4) Using stratification factor, the change for each treatment group (Treatment Period 4 week/8 week – Start of Treatment Period) will be calculated at each visit during the treatment period and the same analysis as in (3) will be performed.
- (5) Analyses same as (1) - (4) are performed, excluding subjects with missing of %FMD (fasting) data at any visit as sensibility analysis.

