5.0 RESEARCH OBJECTIVES AND ENDPOINTS

5.1 Objectives

The objective of this study is to explore the effects of omega-3-acid ethyl esters on vascular endothelial function when administered for 8 weeks, as measured by FMD, in patients with hyperlipidemia.

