6.0 CLINICAL RESEARCH DESIGN

6.1 Clinical research design

< Clinical research design >

This is a multicenter, collaborative, randomized, open-label study designed to explore the effects of administration of omega-3-acid ethyl esters [2 g (2 g PO QD) or 4 g (2 g PO BID) for 8 weeks] on vascular endothelial function, as measured by FMD, in patients receiving a hydroxymethylglutaryl-coenzyme A (HMG-CoA) reductase inhibitor and have concurrent hypertriglyceridemia.

Considering the potential bias by factors that affect FMD between treatment groups, stratified allocation will be performed with fasting TG as a factor.

Research TREATMENT

(1) Study drug:

Omega-3-acid ethyl esters

(2) Dosage regimen

Omega-3-acid ethyl esters will be orally administered [2 g (2 g PO QD) or 4 g (2 g PO BID)] immediately after meal for 8 weeks in patients with hyperlipidemia .

(3) Duration of treatment:

8 weeks

Planned number of research subjects:

40 patients evaluable for the primary endpoint

2 g group: 20 subjects

4 g group: 20 subjects

Number of study sites:

5 to 10 institutions

< Duration of the treatment and number of visits of by subjects >

(1) Duration of treatment:

The duration of the treatment period is 8 weeks. Research subjects should visit the hospital at the time of informed consent at Visit 1 (Day-29 to Day -1 before the start of study drug) and from the start of study drug administration at Visit 2 (Day -15 to Day -1 from the start of study drug administration) to completion of study drug administration [Visit 4 (Week 8)].

CONFIDENTIAL

(2) Number of visits

Observation period: 1 visit

Treatment period: 3 to 6 visits

The FMD measurement during the treatment period will be performed by a physician or laboratory technician who completed the FMD measurement training. Therefore, only for the FMD measurement, subjects are expected to go to a testing laboratory other than the one they normally visit for examinations. In that case, a total of 3 visits for the FMD measurement will be added to the total of 3 visits for examinations from Treatment Period Visit 2 (Day -15 to Day -1 before the start of study drug administration) to Visit 4 (Week 8). Therefore, the number of visits during the treatment period will be a minimum of 3 and a maximum of 6.

[figure not shown]
Figure 6 (a) shows an outline of the clinical research design. Refer to Appendix A for schedule of examinations, observations, and assessments.

Figure 6.a Outline of clinical research design

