6.2 Rationale for the clinical research design

<Rationale>

Since this study aims at exploring the effects of oral administration of omega-3-acid ethyl esters in clinical practice (2 g once a day or twice a day for 8 weeks) on vascular endothelial function, the study was designed as an open-label comparing FMD before and after omega-3-acid administration without including control groups.

< Rationale for the dose and dosing regimen >

In accordance with the approved dosage and administration of omega-3-acid ethyl esters, dose and dosing regimen of omega-3-acid ethyl esters were set at 2 g (2 g PO QD) and 4 g (2 g PO BID) in this study.

< Rationale for the duration of study >

Since improvement of FMD was observed after a 2-month administration of omega-3-acid ethyl esters in the studies conducted outside Japan investigating the effect of omega-3-acid ethyl esters on FMD,⁸⁾ it was considered that the effect of omega-3-acid ethyl esters on FMD can be examined with an 8-week administration and the duration of the treatment period was, therefore, set at 8 weeks in this clinical study.

< Rationale for the planned sample size >

See Section 13.3.

6.3 Premature termination of entire clinical research or premature termination of clinical research at a study site

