13.3 Determination of the number of planned research subject

40 patients evaluable for the primary endpoint

(Omega-3-acid ethyl esters 2 g: 20 patients, Omega-3-acid ethyl esters 4 g: 20 patients)

Exploratory biomarkers will be measured only for the research subjects from whom blood is taken during the observation period after approval of the revised protocol (the 2nd edition) by the committee such as the IEC.

[Rationale for the number of planned research subjects]

The planned sample size is based on the feasibility to explore the effects of omega-3-acid ethyl esters on vascular endothelial function.

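### The objective concerns the drug, but no planned estimate of change in %FMD uses all 40 patients; each unstratified dose-arm interval is about 46% wider than one for the average over both doses

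*SAP*

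**What the plan says.** Protocol 5.1 gives one objective: "The objective of this study is to explore the effects of omega-3-acid ethyl esters on vascular endothelial function when administered for 8 weeks". It mentions no dose. Protocol 6.2 describes the design as "open-label comparing FMD before and after omega-3-acid administration without including control groups". Protocol 6.1 does name the regimens; the study is "designed to explore the effects of administration of omega-3-acid ethyl esters [2 g (2 g PO QD) or 4 g (2 g PO BID".

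Protocol 13.3 plans "40 patients evaluable for the primary endpoint", split evenly between the doses ("Omega-3-acid ethyl esters 2 g: 20 patients, Omega-3-acid ethyl esters 4 g: 20 patients"). The only basis given is feasibility: "The planned sample size is based on the feasibility to explore the effects of omega-3-acid ethyl esters on vascular endothelial function". No SD, effect size, power or target precision is stated.

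For fasting %FMD, SAP 7.1(1) reads: "Summary statistics by treatment group and a two-sided 95% confidence interval for the mean will be calculated at each visit during the treatment period". Items (2) to (4), for change and for the triglyceride strata, are also by treatment group, and item (5) repeats them in complete cases. SAP 7.2 and 7.3.1 import this scheme for the other efficacy endpoints. Protocol 13.1.3 has the same structure. Neither document plans an efficacy estimate over both arms, or a difference between the doses.

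Elsewhere the SAP does use a combined column. For demographics (6.2.1), "the following analysis is performed for each treatment group and all subjects in the analysis set", and 6.1.3.1, 6.1.4.1 and 6.3.1 to 6.3.3 do likewise. Medical history (6.2.2), medications (6.2.3) and the safety tables (section 8) are by group only.

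**The concern.** The objective and the before-after rationale are framed around the drug, and Protocol 13.1 expects the SAP to cover every purpose of the research. As planned, the report gives two 20-patient answers and no drug-level one.

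What is at stake is precision and reading. Suppose both arms improve by 0.45 SD of change. Each arm's interval would then run from just below zero to about 0.92 SD, and the report would show two rows that each include zero. The average over both arms, from the same data, would have an interval clear of zero, but no planned table would show it.

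**Working it through.** **Stated figure.** The documents contain no power or precision calculation. The only figure to reproduce is 20 + 20 = 40.

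**Inputs.** 20 evaluable per arm (Protocol 13.3); two-sided 95% confidence (SAP section 4). Assumptions: equal SD of change in both arms and complete data. The SD is not given, so results are in units of it, and it cancels in the ratios.

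**One arm, as planned.** Half-width = t(0.975, 19)/√20 = 2.0930/4.4721 = 0.468 SD.

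**Average of the two arm means.** With equal weights, the variance is ¼(SD²/20 + SD²/20) = SD²/40. With the pooled within-arm SD (38 df), half-width = t(0.975, 38)/√40 = 2.0244/6.3246 = 0.320 SD.

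**Ratio.** 0.468/0.320 = 1.46. For equal arm sizes from 15 to 25 it runs from 1.48 to 1.45.

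**The 0.45 SD illustration.** One arm: 0.45 ± 0.468 gives −0.02 to 0.92. Average: 0.45 ± 0.320 gives 0.13 to 0.77.

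**What an arm interval loses for its own target.** For the 2 g mean, the 4 g arm can contribute only its SD: 2.0244/√20 = 0.453 SD. 0.468/0.453 = 1.03, a loss of about 3%.

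**Strata.** Cell sizes are not given. Comparing an assumed n per arm with 2n combined (n − 1 and 2n − 1 df):

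| Assumed n per arm in stratum | One arm (SD) | Both arms (SD) | Ratio |
|---|---|---|---|
| 5 | 1.242 | 0.715 | 1.74 |
| 8 | 0.836 | 0.533 | 1.57 |
| 10 | 0.715 | 0.468 | 1.53 |
| 15 | 0.554 | 0.373 | 1.48 |

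**Why the within-arm SD.** If all 40 changes were treated as one sample, a true dose difference of d SD would inflate the SD to √[(38 + 40(d/2)²)/39]: 1.019 at d = 0.5 and 1.109 at d = 1. The ratio would fall to 1.44 and 1.32. The within-arm SD keeps it at 1.46.

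**Difference between doses.** Half-width = 2.0244 × √(1/20 + 1/20) = 0.640 SD.

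**The case against.** The strongest reply is that analysis by dose is legitimate and consistent. Protocol 6.1 names both regimens, patients are randomized between them, and both documents analyse by dose throughout. Two before-after estimates, one per regimen, are a fair reading of the effects of the drug. This stands, and it is why every arm row should be kept.

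A reader might infer that every planned interval is 46% wider than the data allow. The documents do not support that. An arm interval estimates that arm's own mean, and for that quantity it loses only about 3%. The 46% compares it with the interval for a different quantity, the average, and holds only for the unstratified intervals.

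A reader might also cast this as lost power. For a true change of 0.5 SD, a test of zero change would have 56% power in one arm and 87% for the average. But the SAP plans no test and no success rule in an exploratory study sized by feasibility, so the case rests on interval width.

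Nor is the combined column left out of efficacy alone: SAP 6.2.2, 6.2.3 and section 8 are also by group only. The average can also be calculated from the n, mean and SD reported per arm, so no information is destroyed. That makes the addition cheap; it does not put the estimate in the report.

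Finally, averaging can mislead where dose matters. Protocol 4.1 says the drug lowers triglycerides in proportion to dose, so an average over regimens is hard to defend there. This stands and limits the fix to %FMD.

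**Conclusion.** The point holds as a cheap improvement. It is not an error in the planned intervals. The single objective is stated for the drug, yet SAP 7.1 and Protocol 13.1.3 estimate change in %FMD only within 20-patient arms. A drug-level before-after estimate would have a 95% half-width of 0.320 SD against 0.468 SD for one arm, so each unstratified arm interval is about 46% wider. This rests on 20 evaluable patients per arm, equal SDs of change and complete data. No single figure applies to the strata.

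A reader might take the narrower interval as stronger evidence that the drug works. It is not evidence of that on its own: without a control group, the average is subject to the same before-after limits as the arm estimates.

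**What to change.** In SAP 7.1(2), and matching it in Protocol 13.1.3.1, add for fasting %FMD at Week 4 and Week 8:

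- the equal-weight mean of the two arm mean changes, with pooled within-arm variance and a two-sided 95% interval (n₂ + n₄ − 2 df, where n₂ and n₄ are the numbers analysed in the 2 g and 4 g arms; 38 df at 20 per arm);
- the 4 g minus 2 g difference in mean change with its 95% interval, so that readers can judge whether averaging is sensible.

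Name the Week 8 average as the drug-level summary for objective 5.1, and keep all per-arm rows. State that the addition applies to fasting %FMD only. SAP 7.2 and 7.3.1 refer back to 7.1(2), so without that sentence the average would pass automatically to triglycerides, fatty acids and the other lipids. The complete-case repeat in 7.1(5) would pick it up without further wording.

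The cost is a few lines of text and two extra table entries per visit, with no new data, visits or patients. The downside is that the figure averages two regimens and describes neither alone, so it must be read beside the arm rows and the dose difference. If it is added after results have been seen, label it post hoc.
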